8.1.2 Mini Mental State Examination

The Mini Mental State Examination ([Folstein et al, 1975](#)) will be conducted at screening to evaluate the subject's mental status and confirm it meets the inclusion criteria score of 12 to 26 (see [Section 5.1](#)).

8.1.3 Neuropsychiatric Inventory Rating Scale

The NPI (see [Section 8.7.1](#)) will be utilized at screening for confirmation of subject's clinically significant apathy (see [Section 5.1](#)) and to rule out exclusionary comorbid psychiatric diagnoses (see [Section 5.2](#)).

8.2 Efficacy Assessments

Not applicable; pharmacodynamic assessments are discussed in [Section 8.7](#).

8.3 Safety Assessments

Planned time points for all safety assessments are provided in the Schedule of Assessments ([Table 1](#)).

Safety assessments should be performed after all pharmacodynamic assessments have been completed. Assessments should be performed in the following order:

- C-SSRS
- Physical and neurological examinations
- Vital sign measurements
- ECGs

- Blood specimen collection
- Other procedures (eg, concomitant medications, AEs): all other procedures may be obtained before or after blood specimen collection

8.3.1 Physical Examinations

A full physical examination will consist of measurement of height (screening only) and weight and a review of the following body systems: head, ears, eyes, nose, mouth, skin, heart and lung examinations, lymph nodes, gastrointestinal, and musculoskeletal systems.

A full neurological examination will include an assessment of the subject's mental status (level of consciousness, orientation, speech, memory, etc.), cranial nerves, motor (muscle appearance, tone, strength and reflexes), sensation (including Romberg sign), coordination, and gait.

The following guidelines will aid in the standardization of body weight measurements:

- Scales should be calibrated and reliable; scales should be at zero just prior to each subject's weigh-in session
- A subject should void prior to being weighed and be minimally clothed (ie, no shoes or heavy overgarments)

The investigator (or designee) is responsible for performing the physical and neurological examinations. If the appointed designee is to perform these examinations, he or she must be permitted by local regulations and his or her name must be included on the delegation of authority log. Whenever possible, the same individual should perform all physical and neurological examinations.

Any condition present at the post-treatment physical and neurological examinations that was not present at the baseline examination should be documented as an AE and followed to a satisfactory conclusion.

8.3.2 Vital Sign Measurements

Vital signs include systolic and diastolic blood pressures, heart rate, and body temperature. Duplicate blood pressure and heart rate measurements will be obtained sitting/supine (after 5 minutes of rest) followed by a single standing measurement (after 2 minutes of rising from sitting/supine position). The duplicate values will be individually recorded, and the values will be averaged by the sponsor for the time point assessment. At each visit, body temperature will be obtained once, at the time of the first blood pressure measurement.

Any clinically relevant changes occurring during the trial will be recorded in the AE section of the eCRF.

Further details on taking vital sign measurements are provided in the appropriate trial specific manuals.

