9.3. Vital Sign Measurements

Vital signs will include systolic and diastolic blood pressures, heart rate, and body temperature. Duplicate blood pressure and heart rate measurements will be obtained sitting/supine (after 5 minutes of rest) followed by a single standing measurement (after 2 minutes of rising from sitting/supine position). The duplicate values (sitting/supine) will be individually recorded, and the values will be averaged by the sponsor for the time point assessment. At each visit, body temperature will be obtained once, at the time of the first blood pressure measurement. Orthostatic blood pressure parameters are calculated as the average measurement in the sitting/supine position minus the measurement in the standing position for the corresponding parameters, for each visit.

Potential clinically significant values and changes of vital signs parameters are:

- Weight: weight gain or loss >7% from baseline
- Systolic blood pressure (sitting/supine average)
 - Max observed value >160 mmHg
 - Max increase from baseline >20 mmHg
 - Min observed value <90 mmHg
 - Greatest decrease from baseline >20 mmHg
- Orthostatic Systolic Blood Pressure
 - Greatest decrease upon standing compared with sitting/supine position ≥ 20 mmHg
 - Max increase upon standing compared with sitting/supine position ≥ 20 mmHg
- Diastolic blood pressure (sitting/supine average)
 - Max observed value >100 mmHg
 - Max increase from baseline >10 mmHg
 - Min observed value <50 mmHg
 - Greatest decrease from baseline <10 mmHg
- Orthostatic Diastolic Blood Pressure

- Greatest decrease upon standing compared with sitting/supine position ≥ 10 mmHg
- Max increase upon standing compared with sitting/supine position ≥ 10 mmHg
- Heart Rate (sitting/supine average)
 - Max observed value > 120 bpm
 - Min observed value < 50 bpm

Vital signs data including changes from baseline will be summarized through descriptive statistics by visit and treatment group. Potential clinically significant values and changes defined above will be summarized based on the maximum/minimum actual post-baseline values and maximum increase/greatest decrease from baseline. Additionally, all relevant data will be listed for the FAS.

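### Resting blood pressure may be taken sitting or supine at any visit and the SAP pools the two, so changes from baseline and orthostatic flags can mix two manoeuvres

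*Protocol*

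**What the plan says.** Protocol 8.3.2 sets the resting measurement: "Duplicate blood pressure and heart rate measurements will be obtained sitting/supine (after 5 minutes of rest) followed by a single standing measurement". The standing reading comes "after 2 minutes of rising from sitting/supine position". Footnote m of the Schedule of Assessments repeats the either/or wording for every visit, in both the protocol (Table 1) and the SAP (Table 4). On recording, Protocol 8.3.2 says only this: "The duplicate values will be individually recorded, and the values will be averaged by the sponsor for the time point assessment". It then defers detail: "Further details on taking vital sign measurements are provided in the appropriate trial specific manuals". Those manuals are not among the documents.

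SAP 9.3 carries the pooled position into the analysis: "Orthostatic blood pressure parameters are calculated as the average measurement in the sitting/supine position minus the measurement in the standing position". The orthostatic limits are "Greatest decrease upon standing compared with sitting/supine position ≥ 20 mmHg" for systolic and "Greatest decrease upon standing compared with sitting/supine position ≥ 10 mmHg" for diastolic pressure, with matching limits for a rise. The limits for change from baseline are applied to the same sitting/supine average. SAP 4.4.6 takes the last usable reading before the first dose as the safety baseline, with no matching on position. No summary in SAP 9.3 is split by position.

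**The concern.** A fall on standing from sitting and a fall on standing from supine come from two different manoeuvres. If their expected sizes differ, one 20 mmHg limit does not have the same meaning for both. Likewise, if baseline was taken sitting and Week 3 supine, the change from baseline contains any effect of the position as well as any effect of treatment or time.

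Vital sign changes are part of the primary safety endpoint. SAP 9.3 bases its flags on each subject's most extreme post-baseline value, and SAP 4.4.4 lets unscheduled readings count towards a worst case, so a single reading can flag a subject. Arms were planned at 25, and SAP 15 states that the planned sample size was not achieved. A few flags that reflect position could visibly change a table.

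**Working it through.** **Text check.** There is no stated figure in the plan to reproduce on this point.

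- Position allowed: sitting or supine, at every visit (Protocol 8.3.2; Table 1 footnote m).
- Rule to keep one position per subject: none found in either document.
- Position recorded: not mentioned; only the duplicate values are.
- Use in analysis: one pooled resting average, one orthostatic difference and one set of limits (SAP 9.3), with an unmatched baseline (SAP 4.4.6).

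A site that follows the text exactly can change position between visits, and the SAP would subtract the readings as if they were alike.

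**Illustration of size.** All inputs here are assumptions, because the documents give no mean drop, SD or sitting–supine difference. It is also an assumption that the drop is larger from supine.

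*Orthostatic systolic flag at one visit.* P(drop ≥ 20) = 1 − Φ((20 − mean)/SD).

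- Mean 10 from supine, SD 10: 1 − Φ(10/10) = 15.9%.
- Mean 5 from sitting, SD 10: 1 − Φ(15/10) = 6.7%.
- Even mix: (15.9 + 6.7)/2 = 11.3%.
- Range, with mean supine drop 5 to 10 mmHg, SD 10 to 14 mmHg and the sitting drop smaller by 2, 5 or 8 mmHg: supine 6.7% to 23.8%, sitting 1.1% to 19.6%. For the same inputs, the gap between positions runs from about 2 to about 14 percentage points.

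*Resting systolic fall of more than 20 mmHg from baseline, no true change.* P = 1 − Φ((20 − shift)/SD), where shift is the fall produced by the switch of position alone.

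| | SD 10 | SD 14 |
|---|---|---|
| Same position (shift 0) | 2.3% | 7.7% |
| Switch lowers the reading by 5 | 1 − Φ(15/10) = 6.7% | 1 − Φ(15/14) = 14.2% |
| Switch raises the reading by 5 | 1 − Φ(25/10) = 0.6% | 1 − Φ(25/14) = 3.7% |

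Both directions are shown because the documents do not say which position reads higher.

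*Added noise.* If half the orthostatic readings start from each position and the means differ by d, the variance is SD² + d²/4. With SD 10 and d = 8, √(100 + 16) = 10.77, a rise of 7.7% in the SD. With SD 14 and d = 2, √(196 + 1) = 14.04, a rise of 0.3%.

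The noise is thus modest. The absolute flag rates are more sensitive, because they depend on the tail. No rate over several visits is given, since it would need the within-subject correlation, which the documents do not supply.

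**The case against.** The strongest reply is that this rests on silence. The protocol defers to trial-specific manuals, and these or the eCRF may already fix or capture the position. That stands: mixing is permitted by the text, but it is not shown to occur. Even so, SAP 9.3 makes no use of position, whatever the manuals say.

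Three stronger readings are tempting and are not supported.

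- A reader might infer a bias between arms. Treatment is randomised and blinded, so the choice of position should not depend on arm.
- A reader might infer that the orthostatic adverse event of special interest is miscounted. Protocol 8.4.6.1 defines it by symptoms such as syncope, presyncope and dizziness. It uses no measured drop, so position cannot change that count.
- A reader might compound the one-visit rates over the five post-baseline visits at which vital signs are taken. That treats one subject's readings as independent, which overstates the total if they are positively correlated.

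It is also fair to say that the SAP limits are descriptive flags for potential significance, in a trial where formal testing is not the key objective. The illustration compares consistent sitting with consistent supine measurement and an even mix of the two, and it ignores the exclusion of subjects with recent or screening orthostatic hypotension. These limits reduce the weight of the point but do not remove it: the either/or rule gives flag rates that cannot be read without knowing the position.

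**Conclusion.** The point holds in a limited form. The documents allow either resting position at any visit, do not require it to be held or recorded, and pool the two in the analysis. Changes from baseline and orthostatic flags can therefore mix two manoeuvres. The cost is modest extra noise and absolute flag rates that are hard to interpret or to compare with other trials.

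Under the assumed inputs, position alone moves the one-visit orthostatic flag rate by about 2 to 14 percentage points. A 5 mmHg shift from a switch of position moves the resting-fall flag from 2.3%–7.7% to 6.7%–14.2% or to 0.6%–3.7%, depending on direction. These are illustrations only. How often positions actually varied is unknown.

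A separate point arises in the same SAP list. The diastolic limit for the greatest decrease from baseline is printed as <10 mmHg, while its systolic counterpart is >20 mmHg. The inequalities run in opposite directions and must be reconciled.

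**What to change.** **Protocol 8.3.2, or confirmation that the vital signs manual already does this:** require the same starting position for a subject at every visit and record it. With enrolment closed since November 2024 (SAP 1), this helps any remaining visits and later trials. A new eCRF field cannot by itself supply positions for visits already done.

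**SAP 9.3, before database lock:** establish whether position was captured.

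- If it was, keep all visits in the main flags, so that no real drop is hidden. Mark each flag where the position differs from that at baseline. Add a supportive display by position or with a position-matched baseline.
- If it was not, state in the SAP and the report that the orthostatic and change-from-baseline rates pool both positions.

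Reconcile the direction of the diastolic decrease limit at the same time.

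The cost is a sentence in the protocol or manual, one data field where still useful, and one extra display or one sentence in the SAP. The downside is small: with arms planned at 25, a display by position will have sparse cells and should be read as supportive only.

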8.3.3 Electrocardiograms

Electrocardiogram recordings will be obtained after the subject has been supine/semi-recumbent and at rest for approximately 3 minutes. Additional ECGs may be obtained at the investigator's discretion and should always be obtained in the event of early termination. The ECG results will be evaluated at the investigational site to determine the subject's eligibility and to monitor safety during the trial. The investigator (or qualified designee) will review, sign, and date each ECG reading, noting whether or not any abnormal results are of clinical significance. Any clinically relevant changes occurring during the trial will be recorded in the AE section of the eCRF. The ECG will be repeated if any results are considered to be clinically significant. A central ECG service will be used for reading all ECGs in order to standardize interpretations for the safety analysis.

At Screening, a triplicate set of 12-lead ECGs is required to assess subject eligibility. A triplicate set of ECGs is 3 consecutive ECGs collected 1 to 2 minutes apart over a 5-minute period. If, during screening, according to the investigator's judgment, any abnormal ECG finding is deemed medically significant (impacting the safety of the subject or the interpretation of the trial results) or meets an exclusion criterion (see [Section 5.2](#)), the subject should be excluded from the trial. Based on the QT interval as corrected for heart rate by Fridericia's formula (QTcF), a subject will be excluded if the average QTcF interval of the triplicate set of screening ECGs is ≥ 450 msec, as read by the central ECG service.

At all other specified time points in the Schedule of Assessments ([Table 1](#)) where an ECG recording must be performed, only a single ECG is required. If, at the Baseline Visit, the QTcF interval is ≥ 450 msec on the machine reading, consult the medical monitor to determine whether the subject remains eligible to be randomized while awaiting the reading from the central service.

Exclusion criteria for screening do not apply as mandatory discontinuation criteria for subjects who are already randomized. A repeat ECG should be performed to confirm any clinically significant abnormality that is identified in a randomized subject during the treatment period (which will be confirmed by central service read) and, in these cases, the medical monitor should be consulted on the appropriateness of the subject continuing in the trial.

8.3.4 Clinical Safety Laboratory Assessments

See [Section 10.1](#) (Appendix 2) for the list of clinical laboratory tests to be performed and the Schedule of Assessments ([Table 1](#)) for the timing and frequency.

The investigator must review the laboratory report, document this review, and record any clinically relevant changes occurring during the trial in the AE section of the eCRF. The laboratory reports must be filed with the source documents.

All laboratory tests with values considered clinically significantly abnormal during participation in the trial should be repeated until the values return to normal or baseline or are no longer considered clinically significant by the investigator or medical monitor.

If such values do not return to normal/baseline within a period of time judged reasonable by the investigator, the etiology should be identified and the medical monitor notified.

All protocol-required laboratory assessments, as defined in [Section 10.1](#) (Appendix 2), must be conducted in accordance with the laboratory manual and the Schedule of Assessments ([Table 1](#)).

8.3.5 Suicidal Ideation and Behavior Risk Monitoring

Suicidality will be monitored during the trial using the C-SSRS. This semi-structured interview was originally developed to evaluate the link between antidepressants and suicidal behavior and ideation in youth and adverse events from pediatric clinical trials ([Posner et al, 2011](#)). It was designed to quantify the severity of suicidal ideation and behavior. Trial personnel administering the C-SSRS must have completed the appropriate training and have valid certification. Access to training on the scale will be provided by the sponsor or designee.

This trial will use the “Baseline/Screening” and “Since Last Visit” versions of the scale. The “Baseline/Screening” version, which assesses the lifetime experience of the subject with suicide events and suicidal ideation and the occurrence of suicide events or ideation within a specified time period prior to entry into the trial, will be completed for all subjects at screening to determine eligibility. Any subject with active suicidal ideation within the last 6 months, suicidal behaviors within the last 2 years, or who in the clinical judgment of the investigator presents a serious risk of suicide should be excluded from the trial ([Section 5.2](#)).

The “Since Last Visit” C-SSRS form will be completed at all visits after screening. The investigator will review the results of the “Since Last Visit” C-SSRS during the trial to determine whether it is safe for the subject to continue in the trial. If a subject demonstrates potential suicidal ideation associated with actual intent or method or plan as indicated by “YES” answers on item 4 or 5 of the C-SSRS, the investigator will evaluate whether a risk assessment by a qualified mental health professional (or the investigator alone if the investigator is a qualified mental health professional) is needed and whether the subject should continue in or be discontinued from the trial.

8.4 Adverse Events and Serious Adverse Events

The definitions of an AE or SAE can be found in [Section 10.3](#) (Appendix 3).

Adverse events will be reported by the subject (or, when appropriate, by a caregiver, surrogate, or the subject's legally authorized representative).

The investigator and any qualified designees are responsible for detecting, documenting, and recording events that meet the definition of an AE or SAE and remain responsible for following up AEs that are serious, considered related to the IMP or trial procedures, or that caused the subject to discontinue IMP (see [Section 7](#))

8.4.1 Time Period and Frequency for Collecting AE and SAE Information

All AEs and SAEs will be collected from the signing of the ICF until follow-up contact on Day 113 at the time points specified in the Schedule of Assessments ([Table 1](#)).

All SAEs will be recorded and reported to the medical monitor immediately and under no circumstance should this exceed 24 hours, as indicated in [Section 10.3](#) (Appendix 3). The investigator will submit any updated SAE data to the medical monitor within 24 hours of it being available.

Investigators are not obligated to actively seek AE or SAE after conclusion of the trial participation. However, if the investigator learns of any SAE, including a death, at any time after a subject has been discharged from the trial, and he/she considers the event to be reasonably related to the IMP or trial participation, the investigator must promptly notify the sponsor.

8.4.2 Method of Detecting AEs and SAEs

The method of recording, evaluating, and assessing causality of AE and SAE and the procedures for completing and transmitting SAE reports are provided in [Section 10.3](#) (Appendix 3).

Care will be taken not to introduce bias when detecting AEs and/or SAEs. Open-ended and nonleading verbal questioning of the subject is the preferred method to inquire about AE occurrences.

8.4.3 Follow-up of AEs and SAEs

After the initial AE/SAE report, the investigator is required to proactively follow each subject at subsequent visits/contacts. All SAEs will be followed until resolution, stabilization, the event is otherwise explained, or the subject is lost to follow-up (as defined in [Section 7.4](#)). Further information on follow-up procedures is given in [Section 10.3](#) (Appendix 3).

8.4.4 Regulatory Reporting Requirements for SAEs/AESIs

Prompt notification by the investigator to the Sponsor regarding an SAE/AESI is essential so that legal obligations and ethical responsibilities towards the safety of subjects and the safety of an IMP under clinical investigation are met.

The sponsor has a legal responsibility to notify both the local regulatory authority and other regulatory agencies about the safety of an IMP under clinical investigation. The sponsor will comply with country-specific regulatory requirements relating to safety reporting to the regulatory authority, IRB/IEC, and investigators.

Investigator safety reports must be prepared for suspected unexpected serious adverse reactions according to local regulatory requirements and sponsor policy and forwarded to investigators as necessary.

An investigator who receives an investigator safety report describing a SAE or other specific safety information (eg, summary or listing of SAEs) from the sponsor will review, acknowledge, and then file it along with the Investigator's Brochure and will notify the IRB/IEC, if appropriate according to local requirements.

8.4.5 Pregnancy

Details of all pregnancies in female partners of male subjects will be collected after the start of IMP and until the final contact on Day 113.

If a pregnancy in a female partner is reported, the investigator should inform the medical monitor within 24 hours of learning of the pregnancy and should follow the procedures outlined in [Section 10.4](#) (Appendix 4).

Abnormal pregnancy outcomes (eg, spontaneous abortion, fetal death, stillbirth, congenital anomalies, ectopic pregnancy) are considered SAEs.

8.4.6 Adverse Events of Special Interest

All AESIs should be reported according to the procedures and timelines for SAEs (see [Section 10.3.4](#)).

Brief narratives will be written for any subject who reports an AESI.

8.4.6.1 Symptoms Suggestive of Symptomatic Orthostatic Hypotension

- Syncope
- Presyncope requiring stabilization to avoid fall
- Generalized weakness, sensations described as dizziness or lightheadedness, visual blurring or darkening of the visual fields, and, in severe cases, loss of consciousness

8.4.6.2 *Nausea Grade 3*

- Grade 3 nausea, defined as inadequate oral caloric or fluid intake; tube feeding, total parenteral nutrition, or hospitalization indicated

8.4.6.3 *Vomiting Grade 2 or Higher*

- Grade 2 vomiting, defined as vomiting requiring outpatient intravenous hydration or other medical intervention (eg, anti-emetic)

8.4.6.4 *Abnormal Liver Function Tests*

The finding of an elevated value for alanine aminotransferase (ALT) or aspartate aminotransferase (AST) of $>3 \times$ the upper limit of normal (ULN) in combination with either an elevated value for total bilirubin $>2 \times$ ULN or clinical jaundice in the absence of cholestasis or other causes of hyperbilirubinemia is considered to be an indicator of severe liver injury. Investigators must report the occurrence of either of the following as AESI to the sponsor with 24 hours:

- Treatment-emergent value of $>3 \times$ ULN for ALT or AST and $>2 \times$ ULN for total bilirubin
- Treatment-emergent value of $>3 \times$ ULN for ALT or AST and clinical jaundice

8.4.6.5 *Abnormal Dreams/Nightmares*

Either of the following AEs:

- Abnormal dreams
- Nightmares

8.4.6.6 *Adverse Events Potentially Related to Abuse*

A key objective of the Abuse Potential Monitoring Plan (APMP) is to monitor for instances of abuse or diversion of the trial medication and other psychoactive substances.

In addition to monitoring for irregularities in medication handling, AEs that may be suggestive of a developing abuse issue will also receive special attention. As part of the APMP, medication handling irregularities (MHIs) must be reported, and AEs related to abuse potential and AEs involving MHIs must be reported as events subject to additional monitoring (ESAMs), with detailed narratives.

Investigators and site staff at each trial site will be trained on reporting potentially abuse-related AEs (eg, recording a description of the event in the subject's own words in the source documents as well as the eCRF, in addition to the clinical term, and to be aware that a subject's report may encompass more than one event and that these should

be recorded separately). The investigators will be provided with examples of potentially abuse-related AEs and trained on how to handle such events (eg, additional monitoring).

While the investigators will be provided with examples of AE terms as a guide during trial conduct, the analysis of potentially abuse-related AEs will be based on a search by the sponsor of all relevant Medical Dictionary for Regulatory Activities (MedDRA) terms, all verbatim terms, and any open text fields within the AE data to identify text strings suggestive of abuse potential, consistent with US FDA guidance (Guidance for Industry: Assessment of Abuse Potential of Drugs, January 2017).

Complete details, including documenting and reporting procedures, examples of potentially abuse-related terms and guidance for the training of investigators and trial site staff are provided in the APMP.

